2.3. EXPLORATORY OBJECTIVES

The exploratory objectives are:

- To estimate the efficacy of a single IM dose of AZD7442 compared to placebo for the prevention of COVID-19 through Day 366
- To evaluate the single dose pharmacokinetic concentrations of AZD7442 in nasal fluid
- To determine anti-SARS-CoV-2 neutralizing antibody (nAb) levels in serum following a single IM dose of AZD7442 or placebo
- To quantify SARS-CoV-2 viral loads in infected participants treated with a single IM dose of AZD7442 or placebo (Illness Visits)
- To quantify duration of viral shedding in participants with symptomatic COVID-19 treated with a single IM dose of AZD7442 or placebo (Illness Visits)
- To characterize resistance to AZD7442 (Illness Visits) not covered by this SAP
- To assess the biometric profiles associated with COVID-19 using a biosensor in participants treated with a single IM dose of AZD7442 or placebo (Illness Visits)
- To assess symptoms associated with COVID-19 using an e-Diary in participants treated with a single IM dose of AZD7442 or placebo (Illness Visits only)
- To assess additional immune responses following a single IM dose of AZD7442 or placebo not covered by this SAP

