Duration of viral shedding in participants with symptomatic COVID-19 treated with a single IM dose of	Full pre-exposure analysis set, defined as all participants who were randomized, received at least one of the planned injections of IMP, did not have a prior SARS-CoV-2 RT-PCR-positive confirmed COVID-19 infection, and who met the criteria for symptomatic COVID-19 and began Illness Visits following confirmed SARS-CoV-2 infection. Targeted participants will have the following characteristics:	Single dose of AZD7442 (× 2 IM injections, 1 for each mAb component) or placebo	Duration of SARS-CoV-2 shedding in saliva over time.	Not Applicable	Descriptive statistics on number of days of shedding

		Attributes	80		
Label	Definition Population	Treatment Condition of Interest	Variable/ Endpoint	Intercurrent event handling strategy	Population-level summary measure
AZD7442 or placebo (Illness Visits)	benefit from passive immunization with antibodies, defined as having increased risk for inadequate response to active immunization (predicted poor responders to vaccines OR intolerant of vaccine), OR having increased risk for SARS-CoV-2 infection, defined as those whose locations or circumstances put them at appreciable risk of exposure to SARS-CoV-2 and COVID-19.				
Symptoms associated with COVID-19 using an e-Diary in participants treated with a single IM dose of AZD7442 or placebo (Illness Visits only)	Full pre-exposure analysis set, defined as all participants who were randomized, received at least one of the planned injections of IMP, did not have a prior SARS-CoV-2 RT-PCR-positive confirmed COVID-19 infection, and who met the criteria for symptomatic COVID-19 and began Illness Visits following confirmed SARS-CoV-2 infection. Targeted participants will have the following characteristics: Adults ≥ 18 years of age who are candidates for benefit from passive immunization with antibodies, defined as having increased risk for inadequate response to active immunization (predicted poor responders to vaccines OR)	Single dose of AZD7442 (× 2 IM injections, 1 for each mAb component) or placebo	Symptoms recorded by participants in an Illness e-Diary from Illness Visits Day 2 through Day 28.	Not Applicable	Descriptive statistics, including number and percentage of participants with symptoms.

STATISTICAL ANALYSIS PLAN D8850C00002 – ed. V4.0

AstraZeneca 29-Jul-2021

		Attributes	S		

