Day 183	183	138 - 274	
Day 366	366	≥ 275	

Table I: Analysis windows for serum sample for AZD7442 PK, serum sample for SARS-CoV-2 nAbs assessment (PD), and serum sample for exploratory assessments by Visit (Illness Visit Schedule)

Visit	Day Relative to Illness	Visit Window (Illness Day)	
Illness Day 1	≤1	≤ 1	

Illness Day 14	14	8 - 17
Illness Day 21	21	18 - 24
Illness Day 28	28	25 - 35

Table J: Analysis windows for Viral Shedding by Visit (Illness Visit Schedule)

Visit	Day Relative to Illness	Visit Window (Illness Day)
Illness Day 1	≤ 1	≤ 1
Illness Day 3	3	2 - 3
Illness Day 5	5	4 - 6
Illness Day 8	8	7 - 9
Illness Day 11	11	10 - 12
Illness Day 14	14	13 - 17
Illness Day 21	21	18 - 24
Illness Day 28	28	25 - 35

Table K: Analysis windows for nasal adsorption for exploratory assessments by Visit (Illness Visit Schedule)

Visit	Day Relative to Illness	Visit Window (Illness Day)
Illness Day 1	≤ 1	≤ 1
Illness Day 14	14	8 - 20
Illness Day 28	28	21 - 35

For assessments occurring during the Illness Visit Schedule, windows are applied only to illness episodes with laboratory confirmed positive RT-PCR test results. One or more results for a particular human biological samples variable may be obtained in the same visit window. In such an event, the result with the date closest to the expected visit date will be used in the analysis. In the event that two observations are equidistant from the expected visit date, the later observation will be used in the analysis.

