16.3.1.3. Duration of SARS-CoV-2 Shedding in Saliva Over Time (Illness Visits only)

Viral Shedding

An exploratory efficacy endpoint is the duration of SARS-CoV-2 shedding in saliva over time. The analysis will be performed on the full pre-exposure analysis set. Saliva samples for viral shedding will be collected at Illness Visits as described in protocol section 1.3. The number and proportion of participants shedding on Illness Visits planned in the protocol Schedule of Assessments will be summarized. Exact 95% CIs using Clopper-Pearson method for binomial proportions will be computed.

The duration of SARS-CoV-2 shedding in saliva will be calculated as following:

Duration (days) = (Date of Illness Visit when viral shedding first tested as persistently negative or date of last Illness Visit when test was positive, if no negative test is available) – Date of first positive + 1.

The number of days of shedding will be summarized by descriptive statistics.

A listing will be provided for all viral shedding data, regardless of RT-PCR result. Indicators will be included in listings of illness visits to distinguish those with positive RT-PCR results from those with negative RT-PCR results.

• Viral Quantitation

For values reported as lower than the lower limit of quantification (LLOQ), a value equal to half of the limit of quantification will be imputed in viral quantitation summaries. Missing values will not be imputed in viral quantitation summaries.

For the subset of participants who shed, viral quantities as measured by qRT-PCR will be summarized for Illness Visits planned in the protocol Schedule of Assessments. Summary statistics will be presented describing the mean, standard deviation, median, minimum and maximum of Log10 (viral copies/mL) at Illness Visit baseline (Date of first positive) and each post-baseline time-points.

Change and percent change from Illness Visit baseline at each post-baseline time point will also be summarized.

Time weighted change from Illness Visit baseline to each post-baseline time-point is derived on a by-participant basis using the linear trapezoidal rule with all available data from baseline to that specific time-point minus the baseline value. This is defined as (Area Under the Curve [AUC])/number of days – Illness Visit baseline value, between Illness Visit baseline to that specific post-baseline time-point. AUC from Illness Visit baseline to each post-baseline time-point will be reported as well.

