16.3.2. MISSING DATA IMPUTATION METHOD FOR EXPLORATORY EFFICACY ENDPOINTS

No imputation method will be used for exploratory efficacy endpoints.

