APPENDIX 2. PROGRAMMING CONVENTIONS FOR OUTPUTS

DATES & TIMES

Depending on data available, dates and times will take the form yyyy-mm-dd hh:mm:ss.

SPELLING FORMAT

English US.

PAPER SIZE, ORIENTATION, AND MARGINS

The size of paper will be letter and the page orientation will be landscape. Margins will provide at least 1 inch (2.54 centimeters) of white space all around the page.

FONTS

The font type 'Courier New' will be used, with a font size of 8. The font color will be black with no bolding, underlining, italics or subscripting.

PRESENTATION OF TREATMENT GROUPS

For outputs, treatment groups will be represented as follows and in the given order:

Treatment Group	Tables and Graphs	Listings
AZD7442	1	1
Placebo	2	2
Total [1]	5	n/a
Randomized, Not Dosed	n/a	3
Screen Failure	n/a	4

^[1] Not applicable for efficacy tables, safety tables and graphs.

PK analyses will be conducted for participants who receive AZD7442 only. Groups will be represented as follows and in the given order:

Treatment Group	Tables and Graphs	Listings
AZD8895	1	1
AZD1061	2	2
AZD7442	3	3

PRESENTATION OF NOMINAL VISITS

For outputs, analysis visits will be represented as follows and in that order:

Long Name (default)	Short Name
Screening	Scrn
Rescreening	RScrn
Day 1	D1
Day 8	D8
Day 29	D29
Day 58	D58
Day 92	D92
Day 183	D183
Day 366	D366
Day 457	D457

For outputs, analysis visits regarding Illness Visit will be represented as follows and in that order:

Long Name (default)	Short Name
Episode 1 Illness Visit Day X,	1IL-DXX,
X=1,3,5,8,11,14,21,28	X=1,3,5,8,11,14,21,28
Episode 2 Illness Visit Day X,	2IL-DXX,

Long Name (default)	Short Name
X=1,3,5,8,11,14,21,28	X=1,3,5,8,11,14,21,28
Episode Y Illness Visit Day X,	YIL-DXX,
X=1,3,5,8,11,14,21,28	X=1,3,5,8,11,14,21,28
Y = 1, 2, 3, and so on, as applicable	Y = 1, 2, 3,

DESCRIPTIVE STATISTICS

If the original data has N decimal places, then the summary statistics will have the following decimal places:

- Minimum and maximum: N;
- Mean, median, Q1, Q3, lower and upper bounds of two-sided 95% CI: N + 1;
- SD and SE: N + 2

PERCENTAGES

Percentages will be reported to one decimal place. Rounding will be applied, except for percentages < 0.1 but > 0.0 which will be presented as '< 0.1' and percentages < 100.0 but > 99.9 which will be presented as '> 99.9'.

Where counts are zero, no percentages will appear in the output.

P-VALUES

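### Shedding duration counts participants still positive at their last saliva sample as having cleared, which biases the arm comparison when sample series stop early

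*SAP*

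**What the plan says.** The exploratory objective in SAP 2.3 is "To quantify duration of viral shedding in participants with symptomatic COVID-19 treated with a single IM dose of AZD7442 or placebo". SAP 16.3.1.3 computes each duration as an end date minus the date of the first positive, plus one day. The end date has two branches:

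- if clearance is seen: "Date of Illness Visit when viral shedding first tested as persistently negative";
- otherwise: "date of last Illness Visit when test was positive, if no negative test is available".

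The two kinds of value are pooled: "The number of days of shedding will be summarized by descriptive statistics". The estimand table in SAP 2.4 gives the same summary and lists intercurrent events as not applicable. Samples are planned on Illness Days "X=1,3,5,8,11,14,21,28" (SAP Appendix 2), and the last shedding window in Table J of SAP 6.4 closes on Illness Day 35.

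No other section adds a censoring rule for this endpoint. SAP 16.3.2 states "No imputation method will be used for exploratory efficacy endpoints", and 16.3.3 and 16.3.4 rule out sensitivity and supportive analyses. SAP 16.3.1.3 does also plan the number and proportion shedding at each Illness Visit, with Clopper-Pearson intervals.

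**The concern.** For a participant still positive at the last sample, the data show only that shedding lasted at least that long. The rule records it as ending that day. Take two participants first positive on Illness Day 1, one first negative on Day 28 and one still positive on Day 28: both score 28 days. A participant whose series stops while positive on Day 8 scores 8 days, the same as someone first negative on Day 8.

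The endpoint describes duration under AZD7442 and under placebo. With similar sample completeness, the arm that sheds longer has more participants without observed clearance, and each loses more days. The contrast the objective asks for is then understated. The SAP already treats the same problem properly elsewhere: it censors follow-up for the primary endpoint (16.1.4) and plans Kaplan-Meier curves in 16.1.6 and 16.2.7.

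**Working it through.** The SAP gives no expected duration, clearance rate or sample completeness for this endpoint, so there is no figure to reproduce. The durations and loss rates below are assumptions.

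**Inputs.** From the SAP: visit days v = 1, 3, 5, 8, 11, 14, 21, 28, so the gaps are 2, 2, 3, 3, 3, 7, 7; and the duration rule in 16.3.1.3. Assumed: first positive on Illness Day 1; time from then to clearance lognormal with log SD 0.5 and median m = 10 or 15 days; a probability d of leaving saliva sampling for good before each later visit, unrelated to shedding.

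**Formula.** The probability of still being positive at a visit is S(v) = 1 − Φ[(ln(v − 1) − ln m)/0.5], with S(1) = 1. Under the SAP rule a participant scores 1 day plus each gap for which they were positive at its start and sampled at its end. Numbering the later visits k = 1 to 7:

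SAP mean = 1 + Σ (1 − d)^k × S(previous visit) × gap.

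Kaplan-Meier restricted to Day 28 estimates the same sum without the factor (1 − d)^k.

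**Numbers.** S at Days 1, 3, 5, 8, 11, 14, 21:

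- m = 10: 1, 0.999, 0.967, 0.762, 0.500, 0.300, 0.083 (Day 28: 0.023)
- m = 15: 1, 1.000, 0.996, 0.936, 0.791, 0.613, 0.283 (Day 28: 0.120)

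No loss:

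- m = 10: 1 + 2 + 2.00 + 2.90 + 2.29 + 1.50 + 2.10 + 0.58 ≈ 14.4
- m = 15: 1 + 2 + 2.00 + 2.99 + 2.81 + 2.37 + 4.29 + 1.98 ≈ 19.4

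At d = 0.10 the factors are 0.900, 0.810, 0.729, 0.656, 0.590, 0.531, 0.478. The later gaps, where the longer-shedding arm accumulates its extra days, are discounted most.

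| Loss per visit, both arms | SAP mean, m = 10 | SAP mean, m = 15 | SAP difference | Kaplan-Meier difference to Day 28 |
|---|---|---|---|---|
| 0% | 14.4 | 19.4 | 5.1 | 5.1 |
| 5% | 12.2 | 15.9 | 3.8 | 5.1 |
| 10% | 10.3 | 13.1 | 2.8 | 5.1 |

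Differences are taken before rounding. The true unrestricted difference is (15 − 10) × exp(0.5²/2) = 5 × 1.133 = 5.7 days.

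**Where the days go.** At 5% loss, simulation (200,000 per arm) gives 22.5% and 33.4% without observed clearance. Their true means of 15.2 and 23.7 days are recorded as 7.1 and 12.0. That removes 0.225 × 8.1 = 1.8 and 0.334 × 11.7 = 3.9 days from the arm means.

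**Other assumptions.** With log SD 0.8 and median pairs 8/12, 10/15 and 14/21, the simulated SAP difference falls from 3.82, 3.86 and 3.65 days with no loss to 2.14, 2.13 and 1.98 at 10% loss. Kaplan-Meier stays between 3.60 and 3.89. Medians are affected too: for 8/12 at 10% loss, the SAP medians are 8 and 8, against Kaplan-Meier medians of 11 and 14.

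**Unequal loss.** With log SD 0.5, medians 10 and 15, and loss of 10% per visit in the shorter arm and 2% in the longer, the SAP difference is 7.6 days, above the true 5.7. With both medians at 10 and the same unequal loss, the rule gives a difference of 3.1 days where none exists; Kaplan-Meier gives 0.0.

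**The case against.** **The fix changes nothing when sampling is complete.** Correct for the mean. With no loss before Day 28, the SAP mean and the Day-28 restricted mean are identical. A reader might instead compare the SAP figure with an unrestricted mean and infer a far larger error. With assumed medians of 14 and 28 days and log SD 0.6, the SAP difference is 6.6 days against a true 16.7. That gap is not evidence against the rule: Kaplan-Meier restricted to Day 28 also gives 6.6. The shortfall comes from sampling that ends at Day 28, and the longer arm's median would not even be reached.

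**The direction is not guaranteed.** A reader might infer that the rule always shortens the longer-shedding arm most. The unequal-loss results show it need not. Participants who clear are also dated at the first negative visit, up to 7 days after their last positive, which lengthens durations: with no loss, the SAP means exceed the true means by 2.0 and 1.4 days. And if the only censoring is at Day 28 and fewer than half are still positive, the median is untouched.

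**Persistent shedding stays visible.** The planned proportions by visit, the listings and the viral-load summaries would show it. This stands, so it would be too strong to say that the rule hides a treatment effect. It does not correct the reported number of days.

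**Little rests on it.** The endpoint is exploratory, outside the hierarchy in SAP 7.4, and no test of duration between arms is specified. The 24-event row of Table L implies about 0.0098 × 1717 = 17 placebo and 0.0020 × 3433 = 7 AZD7442 cases at the primary analysis, though later cases would add to these. This also stands, and it limits the consequence.

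**Conclusion.** The rule is wrong as written, with limited consequence. It treats right-censored durations as complete, and SAP 2.4 and 16.3.2 to 16.3.4 do not repair this. Under the main assumptions and equal loss, it costs 1.3 of 5.1 days of between-arm difference at 5% loss per visit (5.1 − 3.8) and 2.3 days at 10% (5.1 − 2.8). With complete series it costs nothing in the mean, and only the label is missing.

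The size depends on how often series stop early, which the documents do not say. The supplied protocol is the open-label repeat-dose addendum, not the parent protocol behind the SAP's placebo comparison. Its Table 5 makes saliva collection conditional on operational feasibility, so incomplete series are plausible in that sub-study, but this is only indirect evidence for the parent trial. The Kaplan-Meier figures assume that loss of samples is unrelated to shedding within an arm.

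**What to change.** In SAP 16.3.1.3, define the variable as time from the first positive to the first persistently negative sample. Censor at the last positive sample when no persistent negative follows. State that this covers an isolated negative followed by a final positive, which fits neither current branch: it is not persistent, yet a negative test is available.

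Report by arm:

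- the Kaplan-Meier median with 95% CI where reached;
- the mean restricted to Day 28, labelled as such;
- the number still positive at the last sample.

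Keep the per-visit proportions. The cost is SAP wording and one procedure call, with no new data. The drawback is that the median may not be reached in an arm with many participants still positive, which is why the restricted mean and the count should sit beside it.

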16.3.2. MISSING DATA IMPUTATION METHOD FOR EXPLORATORY EFFICACY ENDPOINTS

No imputation method will be used for exploratory efficacy endpoints.

16.3.3. SENSITIVITY ANALYSES FOR EXPLORATORY EFFICACY ENDPOINTS

No sensitivity analysis will be performed for the exploratory efficacy endpoints.

16.3.4. SUPPLEMENTARY ANALYSES FOR EXPLORATORY EFFICACY ENDPOINTS

No supportive analysis will be performed for the exploratory efficacy endpoints.

17. PHARMACOKINETIC, PHARMACODYNAMIC, AND ADA ENDPOINTS

The PK and ADA secondary endpoints are:

- Serum AZD7442 concentrations
- PK parameters, if data permit
- The incidence of ADA to AZD7442 in serum

The exploratory PK and PD endpoints are:

- AZD7442 nasal fluid concentrations
- Post-treatment geometric mean titers (GMTs) and geometric mean fold rises (GMFRs) for neutralizing antibodies (nAbs) to SARS-COV-2 from baseline value through Day 366 after single IM dose in SARS-CoV-2 nAb (wild-type assay or pseudo neutralization assay)

Other exploratory assays for humoral, mucosal and cellular immune responses may be performed based upon emerging safety, efficacy, and PD data.

17.1. ANALYSIS OF PK, PD, AND ADA ENDPOINTS

17.1.1. SERUM AZD7442 CONCENTRATIONS

Individual AZD7442 (AZD8895 and AZD1061) serum concentration data will be listed and tabulated by mAb component, along with descriptive statistics for the PK analysis set. A figure of serum concentrations by mAb component will also be presented.

Pharmacokinetic exposure (i.e., AUCs) and other PK parameters may be estimated using non-compartmental analysis; this will be optional if data permit. Potential correlation between PK exposure and efficacy/safety response may optionally be explored. Population PK analysis may be performed by the Sponsor and reported in a separate report. The analysis is not covered in this SAP.

To demonstrate that there is no difference between the clonal material and the pooled material, a bioequivalence comparison will be conducted. All participants included in the pharmacokinetic analysis set will be used to evaluate comparability between the clonal and pooled material. This analysis is not covered in this SAP.

17.1.2. THE INCIDENCE OF ADA TO AZD7442 IN SERUM

17.1.2.1. ADA Variables

Serum samples for ADA assessments will be conducted utilizing a tiered approach (screen, confirm, titer), and ADA data will be collected at scheduled visits shown in protocol section 1.3. ADA result from each sample will be reported as either positive or negative. If the sample is positive, the ADA titer will be reported as well. In addition, the presence of nAb will be tested for all ADA-positive samples. The nAb results will be reported as positive or negative. A participant is defined as being ADA-positive if a positive ADA result is available at any time, including baseline and all post-baseline measurements; otherwise the participant is defined as ADA negative.

The number and percentage of ADA-evaluable participants in the following ADA categories in each treatment group will be determined. The number of ADA-evaluable participants in the treatment group will be used as the denominator for percentage calculation.

- ADA positive at any visit (at baseline and/or post-baseline). The percentage of these participants in a population is known as ADA prevalence.
- Treatment-induced ADA positive (positive post-baseline and not detected at baseline).
- Treatment-boosted ADA positive (baseline ADA titer that was boosted by ≥4-fold following drug administration).
- Treatment-emergent ADA positive (either treatment-induced ADA positive or treatment-boosted ADA positive). The percentage of these participants in a population is known as ADA incidence.
- ADA positive post-baseline and positive at baseline.
- ADA positive at baseline and not detected post-baseline.
- Treatment-emergent ADA (TE-ADA) persistently positive, defined as treatment-emergent ADA positive
 participants having at least 2 post-baseline ADA positive measurements with at least 16 weeks (112 days)
 between the first and last positive measurement, or an ADA positive result at the last available assessment.
- Treatment-emergent ADA (TE-ADA) transiently positive, defined as treatment-emergent ADA positive
 participants having at least one post-baseline ADA positive measurement and not fulfilling the conditions for
 TE-ADA persistently positive.
- nAb (to AZD7442) positive at any visit (at baseline and/or post-baseline).

17.1.2.2. ADA Analysis

A summary of the number and percentage of participants who developed detectable ADA to AZD7442 (ADA results to AZD8895 and AZD1061 will be reported separately) by ADA categories (Section 17.1.2.1) in different treatment arms will be presented based on the ADA evaluable analysis set. Descriptive statistics of the maximum

titer will also be presented by ADA category. ADA results and titers will be summarized by visit and treatment group. ADA results will be listed for all participants in the safety analysis set regardless of ADA-evaluable status. ADA titer and nAb data will be presented for samples confirmed positive for the presence of ADA to AZD7442. AEs in ADA positive participants by ADA positive category will be listed.

The effect of ADA on PK, safety, and efficacy will be examined by descriptive summaries if data permits.

